4.3.3 Exploratory outcomes

Effectiveness will be evaluated only on HR+ patients based on the following outcomes, until the end of study observation period:

1. Characterization of first recurrence patterns (location, distribution, size, date)
2. iDFS, defined as the time from neratinib treatment initiation to:
 - a. First ipsilateral invasive breast cancer recurrence
 - b. First regional invasive breast cancer recurrence
 - c. First contralateral invasive breast cancer recurrence
 - d. First distant tumor recurrence
 - e. Death attributable to any cause.
3. DDFS, defined as the time from neratinib treatment initiation to the first distant tumor recurrence or death from any cause.
4. Incidence of CNS metastasis (either isolated or concurrent with other metastatic sites), defined as the time from neratinib initiation to CNS recurrence as first distant recurrence.
5. OS, defined as the time between neratinib treatment initiation (for early breast cancer) and death (due to any cause)

The following key data items will be collected for the **first three** clinical exploratory outcomes:

1. Recurrences after neratinib initiation: date of documented recurrence and site of recurrence, including size and distribution.
 - a. Invasive ipsilateral breast tumor recurrence
 - b. Invasive contralateral breast cancer
 - c. Local/regional invasive recurrence
 - d. Appearance / Occurrence of metastasis /Distant recurrence, including CNS metastasis
2. Date of death and cause of death (related to this cancer, non-breast cancer related, related to another cancer, related to neratinib, other, unknown)
3. Date of last patient visit during follow-up (if applicable)

4.3.4 Subgroups of interest

The following subgroups are of interest, based on patient characteristics at neratinib initiation (index date) or primary diagnosis of breast cancer. Analyses of primary, secondary, and exploratory outcomes may be performed for some or all of these subgroups, subject to pertinence and the number of patients in each subgroup.

1. Nodal status at initial diagnosis (0, 1-3, ≥ 4), Tumor size at initial diagnosis (T1, T2, \geq T3), Stage I vs Stage II+III
 - a. Low risk (Stage I and N- or pCR) vs high risk (Stage II/III or N+ or no pCR)
2. Previous adjuvant or neoadjuvant therapy (Yes/No)
3. Residual disease after neoadjuvant treatment (no pCR)
4. Prior trastuzumab-based regimen (trastuzumab only/ trastuzumab and pertuzumab/ T-DM1)

4.4 DATA SOURCES

Data for each patient will be collected from the date of neratinib treatment initiation up to the end of the study observation period (or date of death, study withdrawal, or lost-to-follow-up, if these come

 Pierre Fabre TEMP CQA 0092 V 2.0 Owning site : CORPORATE QA	Template to use for writing Corporate document, except Corporate policy and form, WORD in english	Page 20/ 29
---	--	-------------

first). Patients lost to follow-up will be censored at the date of their last available medical record. A data collection schedule is provided in Table 1. Data at following timepoints during the Study Observation Period will be collected: (a) at baseline; (b) at the index date; (c) 1 month, 2 months, 3 months, 6 months, 12 months after the index date; and (d) at any additional tumor assessment visits

The source of collected data will include all elements that constitute a reliable source of patient-level information and are available at the center. This includes inpatient medical charts (e.g., consultation notes, discharge summaries, laboratory test results, recorded prescription data and any other documentation of communication with other health care providers). The center investigator will be responsible for ensuring that all the required data is collected and entered into an eCRF. The data will be anonymized during the entry into the eCRF by using an algorithm which generates a patient number without any indication of the patient. This anonymization will be maintained in the database used for statistical analysis.

Key data items that will be collected are listed in section 4.3, Study outcomes.

4.5 STUDY SIZE

Sample size calculation is not applicable, since the study plans to include all eligible breast cancer patients having received neratinib as an extended adjuvant therapy through the EAP in the target European countries.

We estimate the number of patients to be up to 200 patients. Using the table below, the precision estimates for a 95% confidence interval were calculated around proportions ranging from 10% to 50% for a sample size between 150 and 500 patients (see Table 2).

A sample size of 200 patients would allow to assess a category of primary objective (demographic and clinical description of eligible patients) of 10%, 20%, 30%, 40% and 50% of patients with a precision of approximately $\pm 4.1\%$, $\pm 5.5\%$, $\pm 6.4\%$, $\pm 6.8\%$ and $\pm 6.9\%$, respectively.

Table 2. Precision estimates for a 95% confidence intervals around proportions

Precision estimate*	Proportion				
Sample size	10%	20%	30%	40%	50%
150 patients	4.8%	6.4%	7.3%	7.8%	8.0%
200 patients	4.1%	5.5%	6.4%	6.8%	6.9%
250 patients	3.7%	4.9%	5.7%	6.1%	6.2%
300 patients	3.4%	4.5%	5.2%	5.5%	5.6%
350 patients	3.1%	4.2%	4.8%	5.1%	5.2%
400 patients	2.9%	3.9%	4.5%	4.8%	4.9%
450 patients	2.8%	3.7%	4.2%	4.5%	4.6%
500 patients	2.6%	3.5%	4.0%	4.3%	4.4%

*Precision estimates for a 95% confidence interval were calculated using statistical analysis system (SAS)® version 9.4 or higher (SAS Institute, Cary, NC, USA)

 Pierre Fabre TEMP CQA 0092 V 2.0 Owning site : CORPORATE QA	Template to use for writing Corporate document, except Corporate policy and form, WORD in english	Page 21 / 29
---	---	--------------

4.6 DATA MANAGEMENT

A data management plan will be created before the start of data collection and will describe all functions, processes, and specifications for data collection, cleaning and validation to ensure that the data are as clean and accurate as possible when presented for analysis. Data collection and validation procedures will be detailed in the appropriate operational documents.

A study monitoring plan, including for-cause monitoring, that is appropriate for the study design will be developed and implemented. Data quality control (QC) will be performed remotely and at the center level, where permissible according to local regulations, by qualified designated personnel under professional secrecy.

All medical data will be confidential. Pierre Fabre, as the Sponsor of the study and data controller, is responsible for the processing of personal data in accordance with the provisions of Regulation 2016/679/EU of the European Parliament and of the Council of 27 April 2016 on the protection of natural persons with regard to the processing of personal data and the free movement of such data (GDPR), the data collected being for research purposes in the field of health, the legal basis of the processing being the legitimate interest of the data controller.

Data from patient medical records will be entered by the investigator or delegated data entry specialists in the eCRF. Data entered in the eCRF will be sent to a central database via a secure transfer. The qualified designee for data entry must ensure that:

- Data entry is performed in a timely manner
- Data entry is complete and accurate
- All eCRF data are verifiable in the source documentation
- Data queries are resolved and documented by authorized study staff
- All eCRFs are approved with an electronic signature (changes to data previously submitted will require a new electronic signature to acknowledge/approve the changes).

Data entered into the eCRF will be reviewed for consistency by using both automated logical checks (issuing in automatic queries generated by the system) and manual review (issuing in manual checks into the eCRF). For each detected inconsistency, a case report form specific query will be generated (automatic or manual) and the investigator or data entry specialist will be responsible to correct or update any information that is incorrect or incomplete. An audit trail within the system will track all changes made to the data.

All data collected within the eCRF will be approved and electronically signed and dated by the investigator or designee. This approval will acknowledge the investigator's review and acceptance of the data as being complete and accurate.

At study end and before the final statistical analysis, the eCRF and other study data will be locked to further additions or corrections. Locking the study data represents the acknowledgement that all data have been captured and confirmed as accurate.

Quality assurance department representatives from Pierre Fabre and/or Contract Research Organization (CRO) may visit a study center to conduct quality assurance audit and ensure the study is conducted in compliance with protocol, Standard Operating Procedures and all applicable legal requirements (section 4.8).

 Pierre Fabre TEMP CQA 0092 V2.0 Owning site : CORPORATE QA	Template to use for writing Corporate document, except Corporate policy and form, WORD in english	Page 22/ 29
--	--	-------------

4.7 DATA ANALYSIS

4.7.1 General considerations

All statistical analyses will be performed by using statistical analysis system (SAS)[®] version 9.4 or higher (SAS Institute, Cary, NC, USA). A detailed Statistical Analysis Plan (SAP) will be validated by the Sponsor before the database lock. Should there be any major changes in the planned analyses, an amendment to the SAP will be made prior to database lock. Deviations from the SAP after database lock will be outlined in the clinical study report and/or statistical analysis report.

Study outcomes will be analyzed for the full analysis set (comprising of all patients enrolled in the study), and also by country and other predefined subgroups of interest (see section 4.3.4), which will be detailed in the SAP. Where possible, and if allowed by the number of patients, a descriptive analysis of the outcomes across various subgroups will also be performed in an exploratory manner.

4.7.2 Analysis of primary and secondary outcomes

Appropriate summary statistics will be used depending on the nature of the variables, and the number of available and missing data will be specified for each variable. Categorical variables will be presented as frequencies and proportions, and continuous data will be expressed as median, mean, standard deviation, range, and quartiles (Q1 and Q3). The 95% CI will be presented upon relevance to the analysis.

In order to supplement descriptions of neratinib treatment patterns, Kaplan-Meier estimates for treatment persistence, median time to permanent treatment discontinuation, and median time to first treatment modification will also be provided.

4.7.3 Analysis of exploratory outcomes

Time-to-event data (iDFS, DDFS and OS) and cumulative incidence of CNS metastasis will be evaluated using Kaplan-Meier's method and time will be expressed in months. Median survival estimates will be reported along with the 1st and 3rd quartiles, and the corresponding 95% CI. For the description, Kaplan-Meier estimates will be presented with a summary of associated statistics (number of events, number of censored data / median, Q1 and Q3 survival time / estimate rates of patients not presenting the event of interest at 1, 3, 6, 9 ,12 months) including the corresponding two-sided 95% confidence intervals.

Range of follow-up will be provided using Reverse Kaplan-Meier method.

Cox regression analysis may be performed to adjust for predefined baseline covariates, which will be detailed in the SAP.

For OS, the Fine and Gray model will be used to account for the competing risk of disease recurrences.

Where applicable, the Log rank test will be used to compare time-to-event and survival data between subgroups in an exploratory manner.

 Pierre Fabre TEMP CQA 0092 V 2.0 Owning site : CORPORATE QA	Template to use for writing Corporate document, except Corporate policy and form, WORD in english	Page 23/ 29
---	--	-------------

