8.2 Time to Event Analysis

The cumulative incidence of events of interest will be assessed using the Kaplan Meier method and will be presented graphically (Kaplan Meier curve). For Kaplan-Meier, the number of events, number of censored data points, median survival time, Q1 and Q3 survival time and corresponding two-sided 95% CI will be presented. Estimates of the proportion of patients not presenting the event of interest at 3-month intervals (1, 3, 6, 9, 12, 15, 18 months) and the corresponding two-sided 95% CIs will be provided. Censoring rules relative to each event of interest are further detailed in the corresponding analysis sections (see section 13.2).

To determine the potential follow-up time the reverse Kaplan-Meier method will be applied, in this method the events and censors are reversed thus the event of interest (see section 13.2) becomes the censor. For the reverse Kaplan Meier, the number of events, number of censored data points, median follow-up time, Q1 and Q3 follow-up time and corresponding two-sided 95% CI will be presented.

If number of patients is large enough, Cox regression analysis may be performed to adjust for predefined baseline covariates. In this case and for time to Central Nervous System Metastasis, the Fine and Gray model will be used to account for the competing risk of disease recurrences.

Where applicable, the Log rank test will be used to compare time-to-event and survival data between subgroups in an exploratory manner.

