13.2 Time to Event Analysis

All time to event outcomes described in the subsections below will be summarized using the Kaplan-Meier method as described in section 8.2, for FAS and by subgroup EU label; Previous adjuvant or neoadjuvant therapy; Residual disease after neoadjuvant treatment; Prior trastuzumab-based regimen overall; and Prior trastuzumab-based regimen last treatment. (section 8.4)

Patients for whom the event did not occur or who are lost to follow-up, will be censored at the last recorded date that the patient is known to be alive. For patients alive at end of study will be considered the date of study entry, for patients who withdraw consent will be considered the date of consent withdrawal, for patients lost to follow-up will be considered the date of last contact, as collected in the eCRF.

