13.2.4 Overall Survival

OS is defined as the time, in months, from neratinib initiation date (index date) until the date of death (due to any cause).

Table 7 Event and time details for CNS metastasis

Event	Type	Events and censoring dates
Death (all causes)	Uncensored	Date of death
Loss to follow-up	Censored	Date of EOB (section 7.8)
Withdraw consent	Censored	Date of EOB (section 7.8)
No event	Censored	Date of EOB (section 7.8)

OS in months, will be calculated as follows:

- For patients who have an event:
 - $(Date\ of\ death - Index\ date + 1) / 30.4$
- For patients who do not have an event (censored):
 - $(Last\ date\ known\ to\ be\ alive - Index\ date + 1) / 30.4$

Death and corresponding date will be identified from the “Survival Status” page of the eCRF.

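### The protocol prescribes a Fine and Gray model for overall survival with recurrence as the competing risk; that does not estimate overall survival, and the SAP neither clearly withdraws it nor logs a change

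*Protocol*

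**What the plan says.** **Protocol.** Section 4.3.3 gives the endpoint: "OS, defined as the time between neratinib treatment initiation (for early breast cancer) and death (due to any cause". Section 4.7.3 plans two analyses of it. The first is descriptive: "Time-to-event data (iDFS, DDFS and OS) and cumulative incidence of CNS metastasis will be evaluated using Kaplan-Meier's method". The second is a model: "For OS, the Fine and Gray model will be used to account for the competing risk of disease recurrences". The synopsis repeats the model sentence. It carries no condition, whereas Cox regression in the same section is only a possibility.

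**SAP.** Section 13.2.4 keeps the endpoint: "OS is defined as the time, in months, from neratinib initiation date (index date) until the date of death (due to any cause". Its Table 7 has the event row "Death (all causes) Uncensored Date of death" and no row for recurrence. Section 13.2 sets the summary method: "All time to event outcomes described in the subsections below will be summarized using the Kaplan-Meier method as described in section 8.2". On modelling, section 8.2 first says "If number of patients is large enough, Cox regression analysis may be performed to adjust for predefined baseline covariates", and then "In this case and for time to Central Nervous System Metastasis, the Fine and Gray model will be used", again with disease recurrence as the competing risk. Section 7.10 lists the departures from the protocol. Its only entry for section 8.2 is the addition of the 15- and 18-month time points. Fine and Gray is not mentioned there.

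**The concern.** A competing event is one after which the event of interest can no longer occur, or no longer counts. A patient who recurs can still die, and under the OS definition that death counts. If recurrence is coded as the competing event, a patient who recurs and later dies contributes a competing event and no OS event. The subdistribution hazard ratio would then describe the incidence of death without prior recurrence, although it would be labelled overall survival.

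The SAP should have settled this, and its sentence can be read in two ways. On one reading the model now serves CNS metastasis alone, and an analysis that the protocol prescribed without condition has been dropped unrecorded. On the other, Fine and Gray governs any adjusted regression, OS included. The SAP text does not choose between them.

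**Working it through.** **1. The passages side by side**

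| Item | Protocol | SAP |
|---|---|---|
| OS event | Death from any cause (4.3.3) | Death from any cause (13.2.4, Table 7) |
| Role of recurrence in the OS definition | None | None; no row in Table 7 |
| Descriptive method | Kaplan-Meier (4.7.3) | Kaplan-Meier (13.2) |
| Fine and Gray | Named for OS, unconditional (4.7.3, synopsis) | Named for CNS metastasis and for an unspecified case; OS not mentioned (8.2) |
| Change recorded | – | Not in 7.10 |

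**2. What the model would estimate.** Fine and Gray works on the first event. With death as the event of interest and recurrence competing, its target is P(death by *t*, no earlier recurrence). The OS complement is P(death by *t*). The difference is P(recurrence, then death by *t*), which is zero only if nobody dies after recurring. This follows from the model's definition and needs no data.

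**3. The SAP sentence.** The case it refers back to is the preceding sentence on optional Cox adjustment, which names no endpoint. Applied to every adjusted analysis, the sentence would cover OS, and also iDFS and DDFS, where recurrence (for DDFS, distant recurrence) is itself an event (13.2.1, 13.2.2). Applied to CNS metastasis alone, the competing risk makes sense: section 13.2.3 counts CNS metastasis only as first distant recurrence, and a non-CNS first distant recurrence rules that out.

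**4. Size, as illustration only.** The documents state no number of deaths and no OS power, so there is no figure to reproduce.

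Inputs from the documents:
- *N* = 120 (SAP 4.2). This is the whole cohort; an HR+ analysis would have fewer patients.
- Index dates from 01 August 2017 to 31 December 2020 and cut-off 05 July 2022 (SAP 7.1, 7.5). With the SAP's +1 day and 30.4-day month, maximum follow-up is 552/30.4 = 18.2 to 1800/30.4 = 59.2 months, or 1.51 to 4.93 years.
- 2-year iDFS of 93.9% or 91.3%, the two arms of the phase III trial quoted in the protocol background.

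Assumptions not in the documents:
- A share *s* = 5% to 20% of first iDFS events are deaths without recurrence.
- Median survival after recurrence is *m* = 2 to 4 years.
- Times are exponential, entry is uniform, and censoring occurs only at the cut-off.

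Formulas, with λ = −ln(2-year iDFS)/2 and μ = ln 2/*m*:
- Death without recurrence by *t*: *s*(1 − e^(−λt))
- Death after recurrence by *t*: (1 − *s*)[1 − (μe^(−λt) − λe^(−μt))/(μ − λ)]

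For 93.9%, λ = 0.0629/2 = 0.0315 per year. Averaged over follow-up, 1 − e^(−λt) is 0.0959, so 120 × 0.0959 = 11.5 first iDFS events are expected. Deaths counted by the model are 0.05 × 11.5 = 0.6 to 0.20 × 11.5 = 2.3. For 91.3%, λ = 0.0455, with 16.3 first events and 0.8 to 3.3 deaths counted. Adding deaths after recurrence gives:

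| 2-year iDFS | *s* | *m* (years) | All deaths | Counted | Left out |
|---|---|---|---|---|---|
| 93.9% | 5% | 2 | 5.2 | 0.6 | 89% |
| 93.9% | 5% | 4 | 3.3 | 0.6 | 83% |
| 93.9% | 20% | 2 | 6.2 | 2.3 | 63% |
| 93.9% | 20% | 4 | 4.6 | 2.3 | 50% |
| 91.3% | 5% | 2 | 7.3 | 0.8 | 89% |
| 91.3% | 5% | 4 | 4.7 | 0.8 | 83% |
| 91.3% | 20% | 2 | 8.7 | 3.3 | 63% |
| 91.3% | 20% | 4 | 6.5 | 3.3 | 50% |

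A simulation of 2,000,000 patients under the same assumptions agrees to within rounding (50% to 89% left out). At 36 months in the 93.9% case, 1 − OS runs from about 2.3% to 4.6%, against 0.45% to 1.8% for death without recurrence.

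**The case against.** The best defence is that the operative plan already reports OS correctly. Kaplan-Meier is the OS method in both documents, and Table 7 counts every death. Protocol 4.7.3 leaves the covariates for adjustment to the SAP, and SAP 8.2 replaces the reference to OS with one to CNS metastasis, where recurrence as a competing risk is sensible. The broad reading leads to an absurd model for iDFS and DDFS, which counts against it. Regression is optional and depends on patient numbers; with some 3 to 9 deaths in the illustration, an adjusted OS model is unlikely to be run.

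Most of this stands, and it limits the consequence. A reader might infer that the study's reported OS will omit most deaths. The documents do not support that: the Kaplan-Meier estimate is unaffected. A reader might also infer that the SAP definitely carries the model over to OS, iDFS and DDFS. The wording allows that reading but does not require it. What the defence does not remove is the unconditional protocol sentence, the absence of any statement that it is withdrawn, and the silence of section 7.10, which does record a smaller edit to the same SAP section.

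**Conclusion.** The point holds in limited form. The protocol's Fine and Gray instruction for OS contradicts the all-cause definition of OS in both documents. The SAP may have redirected the model to CNS metastasis, but it does so ambiguously and without recording it. Only a Fine and Gray or adjusted OS analysis would be affected, and the SAP makes that optional.

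The contradiction itself rests on the definition of the model and needs no assumption. The 50% to 89% of deaths left out is illustrative: it depends on the assumed share of deaths without recurrence and the assumed survival after recurrence, and it should not be quoted as a property of this study. Severity is minor, because OS is exploratory, the study is descriptive, and no primary or secondary outcome is touched.

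**What to change.** - **SAP 8.2:** state that OS, iDFS and DDFS are analysed by Kaplan-Meier and, if adjusted, by ordinary Cox regression with all defined events counted. State that Fine and Gray applies only to time to CNS metastasis as first distant recurrence, with death and non-CNS first distant recurrence as the competing events. Table 6 now censors death and has no row for a non-CNS first distant recurrence, so annotate it to match for that model.
- **SAP 7.10:** add one line recording that the protocol's Fine and Gray analysis of OS (4.7.3 and synopsis) is withdrawn.
- **Protocol:** correct both sentences at the next amendment.

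The SAP part costs two sentences, a table note and one line, with no new data. Under protocol 4.7.1 it belongs in a SAP amendment before database lock; after lock it would be described in the report as a deviation. The protocol correction goes through ethics review as each committee requires (protocol section 5), so it is best bundled with other changes.

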2 BACKGROUND AND RATIONALE

Background

Breast cancer is the most common type of cancer and the leading cause of cancer mortality in women worldwide. It was estimated that, in 2020, 2.261.419 new cases of breast cancer were diagnosed, and 684,996 deaths were reported due to the disease³. Approximately 15% to 25% of breast cancer tumors are Human Epidermal growth factor Receptor-2-positive (HER2+). Breast cancers with high levels of HER2 are usually more aggressive, with an increased risk of recurrence, reduced survival rates compared to other types of cancer and inadequate treatment response in the metastatic setting⁴⁻⁶. Nevertheless, treatments targeted towards HER2 can be very effective.

For instance, trastuzumab (Herceptin®)⁷ is a monoclonal antibody that specifically binds to the HER2 receptor and induces its internalization and downregulation, thus resulting in inhibition⁸. Trastuzumab is the standard of care for most patients with early-stage HER2+ breast cancer. One year of trastuzumab in the adjuvant setting offers significant benefit in terms of disease-free survival (DFS) and overall survival (OS) in women with early-stage HER2-positive breast cancer^{9,10}. However, breast cancer recurs in 15-24% of patients after a median of 8-11 years¹¹. Extending the duration of trastuzumab therapy to 2 years did not provide significant DFS benefit in patients with early-stage HER2-positive breast cancer, compared to one year of treatment¹².

Alternative therapeutic strategies have been recently approved.

Pertuzumab (Perjeta®)¹ is a humanized monoclonal antibody that binds to a different epitope of the HER2 extracellular domain than trastuzumab. The APHINITY trial results showed a significant improvement in the rates of invasive-disease-free survival (iDFS) in patients with HER2+ breast cancer, when pertuzumab was added to adjuvant trastuzumab and chemotherapy¹³.

Trastuzumab emtansine (T-DM1, Kadcyla®)² is an antibody-drug conjugate of trastuzumab and the cytotoxic agent, emtansine (DM1). Results of the KATHERINE trial showed that the risk of invasive breast cancer recurrence or death was 50% lower with adjuvant T-DM1 than with trastuzumab alone, in HER2+ early breast cancer patients who had residual invasive disease after completion of neoadjuvant therapy¹⁴.

Trastuzumab-based therapy includes treatment with trastuzumab combined with chemotherapy, with or without pertuzumab, or treatment with T-DM1.

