8.4 Examination of Subgroups

The following subgroups are of interest, based on patient characteristics at neratinib initiation (index date) or primary diagnosis of breast cancer. Analyses of primary, secondary, and exploratory outcomes may be performed for some or all these subgroups, subject to pertinence and the number of patients in each subgroup:

- EU label status: Yes, No
 - Yes, defined as, HR+ patients with initiation of Neratinib ≤ 1 year from trastuzumab-based treatment completion in adjuvant setting (EU Label population)
 - No, otherwise
- Pathologic stage (AJCC classification) at primary breast cancer: Stage I, Stage II+III
 - If missing, derived as in 2
- Residual disease after neoadjuvant treatment (pathologic complete response [pCR]): pCR, No pCR

- Risk: Low risk (Stage I or N- or pCR), High risk (Stage II/III or N+ or no pCR)
 - N-, defined as, the electronic case report form (eCRF) nodal status category of NX or N0
 - N+, defined as $N \geq 1$ nodal
- Previous adjuvant or neoadjuvant therapy ⁽²⁾: Neoadjuvant + Post neoadjuvant treatment, Adjuvant only
 - Neoadjuvant + Post neoadjuvant, defined as, at least one neoadjuvant and one adjuvant treatment
 - Adjuvant only, defined as, at least one adjuvant treatment and no neoadjuvant
- Prior trastuzumab-based regimen overall (neoadjuvant or adjuvant): Trastuzumab only, Trastuzumab and Pertuzumab, Trastuzumab emtansine (T-DM1), Other anti HER2
- Prior trastuzumab based regimen the last treatment in adjuvant setting before Neratinib initiation: Trastuzumab only, Trastuzumab and Pertuzumab, Trastuzumab emtansine (T-DM1), Other anti HER2
- Hormone Receptor at Primary Breast Cancer Diagnosis: HR+, HR-
 - HR+, defined as either ER or PR or both are positive
 - HR-, defined as if ER and PR are negative
- Concomitant Corrective Antidiarrheal: Yes, No
- Concomitant Prophylaxis Antidiarrheal: Yes, No
- Initial Dose of Neratinib: <240mg, 240mg, >240mg

Table 2 AJCC staging

Primary tumor (T)	Regional lymph nodes (N)	Distant metastasis (M)	Stage
Tis	N0	M0	0
T1	N0	M0	IA
T0	N1	M0	IB
T1	N1	M0	IB
T0	N1	M0	IIA
T1	N1	M0	IIA
T2	N0	M0	IIA
T2	N1	M0	IIB
T3	N0	M0	IIB
T0	N2	M0	IIIA
T1	N2	M0	IIIA
T2	N2	M0	IIIA
T3	N1	M0	IIIA
T3	N2	M0	IIIA
T4	N0	M0	IIIB
T4	N1	M0	IIIB
T4	N2	M0	IIIB
Any T	N3	M0	IIIC
Any T	Any N	M1	IV

N2 and N3 are not collected in the CRF, this regional lymph node categories will be identified by “ ≥ 4 ” lymph nodes involved.

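### Exploratory log-rank tests across prior anti-HER2 regimens have no strata or named covariates, so a T-DM1 contrast may mix regimen with residual disease

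*Protocol*

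**What the plan says.** - **Test.** Protocol 4.7.3 reads: "Where applicable, the Log rank test will be used to compare time-to-event and survival data between subgroups in an exploratory manner". SAP 8.2 repeats the sentence. Neither names strata, a significance level or a specific contrast.
- **Subgroups.** SAP 13.2 asks for Kaplan-Meier summaries of iDFS, DDFS, time to CNS metastasis and OS by several subgroups, including "Residual disease after neoadjuvant treatment; Prior trastuzumab-based regimen overall; and Prior trastuzumab-based regimen last treatment". Residual disease and regimen stand side by side and are not crossed.
- **Regimen levels.** Protocol 4.3.4 has three: "Prior trastuzumab-based regimen (trastuzumab only/ trastuzumab and pertuzumab/ T-DM1". SAP 8.4 adds a fourth, other anti-HER2.
- **Residual disease.** SAP 8.4 defines it as "Residual disease after neoadjuvant treatment (pathologic complete response [pCR]): pCR, No pCR". Both documents put no pCR in the high-risk definition.
- **Adjustment.** Protocol 4.7.3 says "Cox regression analysis may be performed to adjust for predefined baseline covariates, which will be detailed in the SAP". SAP 8.2 keeps the model optional, makes it depend on patient numbers, and lists no covariate.
- **T-DM1.** The protocol background describes the adjuvant T-DM1 evidence as obtained "in HER2+ early breast cancer patients who had residual invasive disease after completion of neoadjuvant therapy". Nothing states how T-DM1 was used among the early access patients.

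**The concern.** If T-DM1 patients are mostly no-pCR patients while the other regimen groups combine adjuvant-only, pCR and no-pCR patients, the T-DM1 curve can lie lower with no regimen effect at all. The plan records pCR status and treats its absence as high risk, yet does not use it in the regimen comparison.

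The two safeguards that the protocol points to are not in the SAP. The Cox covariates are not listed. Protocol 4.10 also defers the handling of bias to the SAP, but no SAP section deals with confounding of regimen. With the few events expected, the Cox model may well not be fitted, and the unadjusted log-rank could be the only regimen comparison reported.

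The rationale in both the synopsis and protocol section 2 rests on patients who had pertuzumab or T-DM1 before neratinib. Readers are therefore likely to look closely at these curves and any p-value beside them.

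**Working it through.** **1. The plan's own figure.** The only design figure is the half-width of a 95% CI for a proportion, 1.96 × √(p(1−p)/n).
- n = 200: 4.16 points at 10% and 6.93 at 50% (stated 4.1 and 6.9).
- n = 120: 5.37 and 8.95 (stated 5.4 and 9).

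The table reproduces to within 0.1 point. It says nothing about a log-rank test, for which no power or event count is given.

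**2. Inputs from the documents.**
- Index dates run from 1 August 2017 to 31 December 2020, with cut-off 5 July 2022 (SAP 7.1, 7.5). Potential follow-up is 551/30.4 = 18.1 to 1799/30.4 = 59.2 months.
- SAP 4.2 expects 120 patients.
- Protocol section 2 gives 93.9% two-year iDFS on neratinib in the pivotal trial. Taken as a constant hazard: −ln(0.939)/24 = 0.00262 per month.

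**3. Expected iDFS events.** With censoring uniform over 18.1–59.2 months, the mean event probability is 1 − (e^(−0.0475) − e^(−0.1553))/(0.00262 × 41.1) ≈ 0.096. That gives 11.5 events for N = 120 and 8.1 for N = 84. N = 84 is an assumed smaller analysis set; the documents give no HR+ count.

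**4. Assumptions not in the documents.** T-DM1 share 25%; no pCR in 80–100% of T-DM1 patients and 15–30% of others; hazard ratio of no pCR against the rest 2–3; no regimen effect.

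**5. Apparent T-DM1 hazard ratio from mixing alone.** With a and b the no-pCR shares in T-DM1 and other patients, and h the no-pCR hazard ratio, the value at the start of follow-up is (a·h + 1 − a)/(b·h + 1 − b).
- a = 0.8, b = 0.3, h = 2: 1.8/1.3 = 1.38.
- a = 0.9, b = 0.3, h = 2: 1.9/1.3 = 1.46.
- a = 1, b = 0.15, h = 3: 3/1.3 = 2.31.

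The distortion is partial: in the second case it is 1.46, not the full 2.

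**6. Simulated rejection at two-sided 5% with no regimen effect.**

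| Test | Unstratified | Stratified by residual disease |
|---|---|---|
| Four regimen levels, as in SAP 8.4 (assumed shares 40/25/10/25%) | about 6–18% | about 4–6% |
| T-DM1 against the rest | about 8–32% | about 4–6% |

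With about 8 events the chi-square approximation for four levels is rough, and the stratified rate can come out slightly higher. The strata here were no pCR against all others.

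A second two-group grid assumed 20–33% T-DM1, no pCR in 70–100% against 30–50%, and hazard ratio 1.5–3. At N = 120 it gave about 6–22% unstratified and 4–5% stratified. The middle case (90% against 30%, hazard ratio 2) gave about 11%.

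**7. What remains after stratifying.** The no-pCR share of events is w·h/(w·h + 1 − w), with w = 0.25a + 0.75b.
- a = 1, b = 0.15, h = 2: w = 0.3625, share 0.725/1.3625 = 0.53, or about 4 of 8.1 events.
- a = 1, b = 0.3, h = 3: w = 0.475, share 1.425/1.95 = 0.73, or about 8 of 11.5 events.

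Even with all 11.5 events, Schoenfeld power for a true regimen hazard ratio of 2 is only about 15–20%.

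**The case against.** The strongest reply is that this is a descriptive study. Protocol 4.3 calls its outcomes purely descriptive, no objective compares regimens, and regimen is one of several subgroups that may be analysed if numbers permit. The log-rank is conditional and exploratory, and SAP 13.2 itself asks only for Kaplan-Meier summaries. All of this stands. A reader might infer from the rationale that the regimen comparison is what the study was set up for. The documents do not support that: the rationale makes these patients a population of interest, not a planned contrast.

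The link between T-DM1 and residual disease is also inferred from a cited trial's population. That stands too, and it makes every size above conditional. In addition, T-DM1 against the rest is not a planned contrast, so the four-level figures are closer to the plan.

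Residual disease is already a separate time-to-event subgroup, and Protocol 4.10 admits confounding in general terms. Neither separates regimen from residual disease. Calling a test exploratory does not make a confounded p-value easier to interpret.

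**Conclusion.** The point holds in a limited form. The SAP permits unstratified regimen tests, names no adjustment covariates, and leaves unused a recorded factor that it classes as high risk. Under the stated assumptions, false rejection rises from about 4–6% to about 6–18% for the four-level test and 8–32% for T-DM1 against the rest. At the mild end the excess is negligible. The actual size depends on the T-DM1 and pCR shares in this cohort, which the documents do not give.

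A reader might go further and say that the test measures residual disease instead of regimen. That is too strong: it mixes the two, and the argument does not reach trastuzumab against trastuzumab plus pertuzumab. Nor does anything calculated here support stage stratification for the neoadjuvant/adjuvant subgroup.

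The change is worth making because it is cheap. It affects exploratory results only.

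**What to change.** In SAP 8.2 and 13.2, for "Prior trastuzumab-based regimen overall; and Prior trastuzumab-based regimen last treatment":

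1. Either stratify the log-rank by neoadjuvant outcome in three strata (adjuvant only, neoadjuvant with pCR, neoadjuvant without pCR) or, if events are too few, show the regimen curves without p-values. The first stratum keeps adjuvant-only patients, who have no pCR status.
2. In both cases, show T-DM1 against trastuzumab with or without pertuzumab within no-pCR patients.
3. State confounding by residual disease as a limitation of the regimen results.
4. If the Cox model is kept, list its covariates, as the protocol promised.

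The cost is SAP wording and a stratification option in the existing software, with no new data. Protocol 4.7.1 allows a SAP amendment before database lock; after lock, the change would be reported as a deviation. The downside is power: with only about 4–8 events in the no-pCR stratum under the assumptions above, a stratified test will detect little, and a non-significant result should not be read as equivalence of regimens.
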